8.3.3 Medical history

Medical history data will be coded using MedDRA® version 25.1 or later. The number and percentage of subjects with each medical history and surgery will be summarized by System Organ Class (SOC) and Preferred Term (PT) by dose levels and total for subjects in the Safety Set. The summary will be sorted alphabetically by SOC and PT within SOC.

8.4 Efficacy analysis

There are no efficacy endpoints for this trial.

The primary objective is to describe the safety and tolerability of BNT165b1; the endpoints used for this are described in Section 8.5.2, Section 8.5.3 and Section 8.5.4 below.

8.5 Safety analyses

The primary endpoints of this trial include local reactions, systemic events, AEs, SAEs and MAAEs.

Other Safety data that will be summarized includes physical examinations, vital signs, height, body weight, electrocardiogram (ECGs) and clinical safety laboratory assessments (including Hematology and Clinical chemistry). All safety analyses will be based on the safety set and will be summarized by each dose level, combined placebo and visit if applicable.

Page 18 of 36 Version: 3.0 Date: 08 MAY 2024

8.5.1 Exposure to IMP

The number and percentage of subjects receiving trial doses will be tabulated by DL for the subjects in safety set.

For each dose, the following will be tabulated:

- Subjects receiving the dose,
- Subjects receiving the complete dose,
- Subjects receiving an incomplete dose,
- Reasons for receiving an incomplete dose,
- For dose 2 and 3 only: reason for not having received the dose.

8.5.2 Local reactions

The below subsections describe the analysis of solicited local reactions collected via the e-Diary and the analysis of acute local reactions as assessed by the investigator.

Delayed injection site reactions occurring between 7 days and 14 days after each dose will be solicited during a phone call that will occur 14 days after each dose. This data will be listed only.

8.5.2.1 Solicited local reactions

Local reactions assessed and reported in the e-diary are pain at the injection site, erythema/redness and induration/swelling from Day 1 through Day 7 after trial IMP dose, where Day 1 is the day of IMP injection. A subject is deemed to have had a local reaction if they report the reaction as "yes" on any day (Day 1 through Day 7).

Solicited local reactions will be categorized as mild, moderate, severe or potentially life-threatening) and graded from 1 to 4, as described in Table 4. The categories and grades are based on the FDA Guidance for Industry: "Toxicity Grading Scale for Healthy Adult and Adolescent Volunteers Enrolled in Preventive Vaccine Clinical Trials"⁴.

Any local reaction of Grade 3 or higher will be confirmed by the investigator along with an assessment if it meets the definition of Grade 4.

Page 19 of 36 Version: 3.0 Date: 08 MAY 2024

Table 4: Local reaction grading scale

		Moderate (Grade 2)	Severe (Grade 3) °	Potentially life-threatening (Grade 4) ^c
Pain at the injection site	Does not interfere with activity	Interferes with activity	Prevents daily activity	Emergency room visit or hospitalization for severe pain
Erythema / redness ^a	2.5 cm to 5.0 cm	>5.0 cm to 10.0 cm	>10 cm	Necrosis or exfoliative dermatitis
Induration / swelling ^b	2.5 cm to 5.0 cm	>5.0 cm to 10.0 cm	>10 cm	Necrosis

- In addition to grading the measured local reaction at the greatest single diameter, the measurement will be recorded as a continuous variable.
- b. Induration/swelling should be evaluated and graded using the actual measurement.
- c. Investigator or medically qualified person confirmation is required.

For subjects recording at least one local reaction from Day 1 through Day 7 after IMP injection and for each specific local reaction mentioned in Table 4:

- The maximum severity grade is equal to the highest graded local reaction within the
 recording period. In case of a discrepancy between the subject and investigator
 assessment of severity, the confirmed assessment of the investigator will be used
 for analyses and a comment in the listings will be provided explaining the
 discrepancy.
- Duration will be calculated in days as the difference from the start of the reported event to the resolution of the event, inclusive. If an event resolves and occurs again within the reporting period of the eDiary, the duration will be calculated for each separate event and the maximum duration will be used for the analysis.
- Any missed assessment will be considered as "no reaction". (e.g., if a subject has grade 1 headache on day 1 and 2, missing data on day 3 and 4 and grade 2 headache between day 5 and 7, this should be considered as 2 separate headache events, one of 2 days duration and one of 3 days duration. The maximum duration (3 days in this example) and the maximum severity (grade 2 in this example) would be used for the analysis.).
- For events that persist beyond Day 7, the duration of the reactogenicity event will be derived using the start and the end date of the AE (as recorded on the AE page).
- Onset day, defined as the first day of reporting any severity, will be derived for each recorded local reaction.

A reactogenicity overview summary will include the subjects with

- Any local reaction within 7 days of IMP injection
- Any local reaction that persisted beyond 7 days of IMP injection

Page 20 of 36 Version: 3.0 Date: 08 MAY 2024

Analyses in the overview summary will be provided for reactions of any grade and for reactions of grade ≥3. Analyses will be provided within 7 days of each IMP injections and overall regardless of the number of injections.

The number and percentage of subjects reporting local reactions (pain at the injection site, erythema/redness, induration/swelling) within 7 days after IMP dose will be summarized by maximum severity and cumulatively regardless of the severity. This summary will include categories "Any", "Grade 1", "Grade 2", "Grade 3" and "Grade 4".

All local reaction summaries will be based on the safety set but excluding subjects without any e-diary data throughout the 7 days after vaccination.

In addition, local reactions will also be summarized by:

- Maximum duration (days) of each local reaction after each IMP injection and overall regardless of the number of injections
- Onset day of each local reaction after each IMP injection and overall regardless of the number of injections

For analyses overall across all injections, the subject will only be counted once for each local reaction reported.

Bar charts with the number of subjects for each local reaction throughout 7 days after each dose will be plotted. The bars will be divided into severity categories to highlight the proportions of subjects by maximum severity. In addition, listing of subjects in the safety set with reported local reactions, will be provided.

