8.2.6 Subject e-diaries for assessment of reactogenicity (local and systemic reactions)

Subject e-diaries will be issued, trained, and collected by trial site personnel at the visits given in the SoA (Section 1.3).

Subjects will be asked to:

- Report reactogenicity (incl. oral body temperature) daily for 7 d after each IMP dose using an e-diary.
- Report the use of antipyretic/analgesic medication to treat symptoms associated with IMP administration for 7 d after each IMP dose using an e-diary.
- Record the worst grade for each symptom at approximately the same time every evening.
- Contact the site if they experience any severe or potentially life-threatening reactogenicity events.

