8.2.6.1 Assessments of intensity for local reactions

Pain (perceived) at the injection site will be assessed as absent, mild, moderate, severe, or potentially life-threatening, according to the grading scale in Table 2.

Erythema/redness and swelling/induration will be measured and recorded in centimeters and then categorized during analysis as absent, mild, moderate, severe or potentially life-threatening, based on the grading scale in Table 2.

Page 45 of 82 Version: 4.0 Date: 13 FEB 2023

Any local reaction of Grade 3 or higher will be confirmed by the investigator along with an assessment if it meets the definition of Grade 4.

Table 2: Local reaction grading scale

	Mild (Grade 1)	Moderate (Grade 2)	Severe (Grade 3) °	Potentially life-threatening (Grade 4) °
Pain at the injection site	Does not interfere with activity	Interferes with activity	Prevents daily activity	Emergency room visit or hospitalization for severe pain
Erythema / redness ^a	2.5 cm to 5.0 cm	>5.0 cm to 10.0 cm	>10 cm	Necrosis or exfoliative dermatitis
Induration / swelling ^b	2.5 cm to 5.0 cm	>5.0 cm to 10.0 cm	>10 cm	Necrosis

- In addition to grading the measured local reaction at the greatest single diameter, the measurement should be recorded as a continuous variable.
- b. Induration/swelling should be evaluated and graded using the actual measurement.
- c. Investigator or medically qualified person confirmation is required.

Source: Based on the US FDA "Toxicity Grading Scale for Healthy Adult and Adolescent Volunteers Enrolled in Preventive Vaccine Clinical Trials".

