- Record the worst grade for each symptom in the e-diary at approximately the same time every evening on the day of IMP injection and then every day in the evening for a total of seven consecutive days.
- Measure their body temperature using the provided device and record their body temperature in the e-diary every day including the day of IMP injection.
- To assess any solicited local reactions at the injection site as described in Section 8.2.6.1 and solicited systemic reactions as described in Section 8.2.6.2.
- To contact the site immediately in case of severe or potentially life-threatening reactogenicity events.

Clinical Trial Protocol Trial number: BNT165-01 Page 47 of 82 Version: 4.0 Date: 13 FEB 2023

Investigators will review subject-reported e-diary data at the times given in the SoA (Section 1.3).

Only an investigator or medically qualified person is able to confirm Grade 3 or a potentially life-threatening Grade 4 event for recording in the EDC system.

If a trial subject experiences confirmed Grade 4 reactogenicity, the investigator must immediately notify the sponsor and, if it is determined to be related to the administration of IMP, further IMP administration will be discontinued in that trial subject (see Section 7.1).

If a trial subject experiences a potential Grade 3 reactogenicity or higher, the subject must immediately notify the investigator or some other medically qualified person, who will then confirm the grading, the confirmed Grade 4 reactogenicity will be recorded by the investigator as an SAE. Data for solicited Grade 3 or lower events do not need to be reported separately by the investigator as AEs in the EDC system, unless they are reported as an unsolicited event or extends beyond the 7 d.

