8 STATISTICAL ANALYSES

8.1 General considerations

In general, all summaries will be displayed by individual vaccine DL and combined placebo. A total group, combining all subjects on placebo and active vaccine, will be presented in addition for accounting (subject disposition), demographics and other baseline characteristics and protocol deviations as applicable unless otherwise specified.

No formal statistical comparisons between vaccine DL of BNT165b1 and placebo will be performed. Missing data, other than that described for partial or missing dates for AEs/concomitant medications/vaccinations (as described below) will not be imputed.

Continuous variables will be summarized using the following descriptive statistics: number of subjects with non-missing data (n), mean, SD, median, minimum (min) and maximum (max).

Categorical variables will be summarized by absolute and relative frequencies (n and %) of subjects in each category and the number of subjects with missing data ('missing' category will be presented if there is one or more missing value).

For event-driven occurrence data (e.g., adverse event, concomitant medication, etc.) percentages will be based on the number of subjects in the analysis set (N). For reported visit data (e.g., lab etc.) percentages will be based on the number of subjects with non-missing values (n).

The rates of binary endpoints such as safety variables (systemic and local reactions) will be provided.

Page 13 of 36 Version: 3.0 Date: 08 MAY 2024

All data collected during the trial will be listed based on safety set unless otherwise specified. The trial day will be presented as appropriate. Listings will be sorted by dose level, site number, subject number, and date of assessment or date of onset (if applicable).

All trial data will be presented at the visit as assigned in the Case Report Form (CRF). No windowing of data for the purposes of assigning to a visit will occur. Unscheduled assessments will not be included in summaries/analysis but will be included in the listings.

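### Does counting every diary yes as a local reaction, with no row for redness or swelling under 2.5 cm, undermine the reactogenicity tables?

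*SAP*

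**What the plan says.** SAP 8.5.2.1 (Solicited local reactions) takes presence from the diary: "A subject is deemed to have had a local reaction if they report the reaction as" *yes* on any of Days 1 to 7, with no size condition. Severity comes from Table 4 of the SAP, where Grade 1 for redness and for swelling starts at 2.5 cm; pain has no such floor. Reactions within 7 days of a dose "will be summarized by maximum severity and cumulatively regardless of the severity", in the rows *Any* and Grades 1, 2, 3 and 4.

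The same section adds an overview: "Analyses in the overview summary will be provided for reactions of any grade" and separately for Grade 3 or higher. It also gives an onset rule: "Onset day, defined as the first day of reporting any severity".

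Protocol 8.2.6.1 describes redness and swelling differently. They "will be measured and recorded in centimeters and then categorized during analysis as absent, mild, moderate, severe or potentially life-threatening". Neither document says that a mark below 2.5 cm is absent.

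On what the subject enters, Protocol 8.2.6 gives the instruction "Record the worst grade for each symptom at approximately the same time every evening", and Protocol 8.2.7 has site staff remind subjects: "To assess any solicited local reactions at the injection site as described in Section 8.2.6.1". For categorical summaries in general, SAP 8.1 says that a missing "category will be presented if there is one or more missing value".

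**The concern.** Presence and grade come from two sources that need not agree. A subject who reports redness of 1.5 cm has a reaction under the *yes* rule but no grade under Table 4. That subject would be counted in *Any*, sit in no grade row, have no segment in a bar chart split by severity, and have an uncertain onset day if onset needs a severity. The general missing category does not strictly help, because a measured 1.5 cm is not a missing value.

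The protocol's list of categories includes absent, which the SAP omits. If marks below 2.5 cm were meant to be absent, the two documents would give different rates, and SAP Appendix 1 records no change from the protocol. Frequency of solicited local reactions is the first primary estimand listed, and the groups are small enough for one subject to shift a percentage visibly. Diarrhea seems to have the same problem, since its Grade 1 starts at 2 loose stools and SAP 8.5.3 derives presence as for local reactions.

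**Working it through.** The plan states no figure on this point, so there is none to reproduce. The check applies the written rule and then sizes its effect.

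**Inputs.** Presence rule, cut-offs and table rows: SAP 8.5.2.1 and Table 4. Group sizes: 16 vaccine and 4 placebo per cohort (SAP 3.2), with placebo pooled over three cohorts (SAP 8.1), 3 × 4 = 12.

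**Step 1: does the mismatch arise?** Take an illustrative group of 16. Eight report *yes*, with largest diameters 1.0, 2.0, 2.4, 2.5, 5.0, 5.1, 10.0 and 10.1 cm; the other eight report *no*.

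| Row | Subjects | Count |
|---|---|---|
| *Any* (yes rule) | all eight | 8/16 = 50.0% |
| Grade 1 (2.5 to 5.0 cm) | 2.5, 5.0 | 2 |
| Grade 2 (>5.0 to 10.0 cm) | 5.1, 10.0 | 2 |
| Grade 3 (>10 cm) | 10.1 | 1 |
| Grade 4 | none | 0 |
| Sum of grades | | 5/16 = 31.3% |

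The excess is 8 − 5 = 3, exactly the marks at 1.0, 2.0 and 2.4 cm. Showing those three separately gives 3 + 5 = 8. Treating them as absent would give *Any* = 5. Both tables add up; they differ only in what is called a reaction.

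**Step 2: size per subject.** 1/16 = 6.25 points per dose level; 1/12 = 8.33 points for pooled placebo.

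**Step 3: how likely is at least one such subject?** The documents give no rate of marks that never reach 2.5 cm. For an assumed rate p per dose, the chance is 1 − (1 − p)^n.

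| Assumed p | n = 16 | n = 12 |
|---|---|---|
| 2% | 28% | 22% |
| 5% | 56% | 46% |
| 10% | 81% | 72% |
| 20% | 97% | 93% |

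These chances hold only if the e-diary accepts a *yes* below 2.5 cm. If it does not, they are all zero.

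**Step 4: which outputs are touched?**

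- *Overview.* As listed in SAP 8.5.2.1 it reports any local reaction, not redness or swelling separately, so it cannot contradict the severity table on those rates. Even if its any-grade row were read as graded reactions only, it would differ just for subjects with no graded local reaction at all. Protocol 4.2 cites injection site pain above 80% for the related vaccine. At 80%, 16 × (1 − 0.80) = 3.2 of 16 vaccinees have no pain; at an assumed 50%, 8 of 16.
- *Diarrhea.* Protocol 8.2.6.2 has systemic symptoms assessed on a scale that includes absent, and neither document says a stool count is recorded and graded later. The mismatch is not shown here.
- *Acute reactions.* Under SAP 8.5.2.2 the investigator grades directly from Table 4; the diary *yes* rule is not stated to apply.
- *Duration.* It runs from reported start to resolution and needs no grade.
- *Pain, Grade 3 or higher counts, pausing rules, listings.* None depends on the 2.5 cm floor.

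What remains is the severity table, the bar charts and the onset day, for redness and swelling only.

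**The case for a change.** The strongest case for a change is that two readings of a primary endpoint can both be defended. One follows the *yes* rule. The other notes that the SAP grades solicited local reactions from 1 to 4 and that the protocol sorts redness and swelling by measured size, with absent as the only category left for a small mark. Two programmers could then produce different *Any* rates. Fever shows that the SAP can align the two when it wants to: presence and Grade 1 both start at 38.0°C. A clarifying sentence would cost almost nothing.

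Part of this stands. The SAP does not say how an ungraded *yes* is displayed, and the protocol's absent category sits awkwardly beside the *yes* rule. The instruction to record a worst grade does not prove that the diary has a floor, since Protocol 8.2.6.1 puts the grading of these two reactions at the analysis stage.

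The step from there to a defect does not stand. For presence, the SAP is explicit: a *yes* counts, and *Any* is taken regardless of severity. This agrees with the estimand, which concerns reactions recorded, and with Protocol 9.4.2, which counts subjects reporting a reaction. That a mark below 2.5 cm is absent is an inference written in neither document. Moving presence to 2.5 cm would be a choice on which reasonable statisticians differ, and it has a cost: a subject whose only mark is smaller would have a reported duration but no presence and no onset.

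**Conclusion.** No change to the plan follows. *Any* is defined by the diary *yes*, and the grade rows by Table 4. If sub-threshold marks are reported, the gap between *Any* and the sum of the grades is their count, visible in the table. An analyst would ordinarily add a footnote or a below-Grade-1 line when laying out the table, and would date onset from the first *yes*. SAP 8.1 provides for listing all collected data, so a reader who prefers the size-based count can derive it from the recorded diameters.

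The effect is 6.25 points per affected vaccinee within a dose level and 8.33 points per affected placebo subject, confined to redness and swelling. Those steps assume full groups of 16 and 12; excluding subjects without diary data would make them slightly larger. The number affected is unknown, because neither the e-diary's entry rule nor the rate of small marks is in the documents. The trial is descriptive with no hypothesis test, and the affected rows feed no pausing rule or Grade 3 or higher count. This is a matter of presentation that changes no conclusion.

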8.5.2.2 Acute local reactions

Investigators will assess acute local reactogenicity at the visits given in Section 10.4. Investigators will grade and record acute local reactions as described in Table 4. The number and percentage of subjects reporting acute local reactions (pain at the injection site, erythema/redness, induration/swelling) up to one hour after IMP dose will be summarized by severity and cumulatively regardless of the severity. This summary will include categories "Any", "Grade 1", "Grade 2", "Grade 3" and "Grade 4". The number and percentage of subjects reporting local reactions (pain at the injection site, erythema/redness, induration/swelling) prior to administration of IMP dose will be summarized in a similar manner.

8.5.3 Systemic reactions

The systemic reactions assessed and recorded in the e-diary are vomiting, diarrhea, headache, fatigue/tiredness, Myalgia-muscle pain, Arthralgia-joint pain, chills and fever from Day 1 through Day 7 inclusive, where Day 1 is the day of each IMP injection. The derivations for systemic reactions will be handled similar to the way local reactions are handled for presence of event, severity level, duration, and onset day.

Fever is defined as an oral temperature $\geq 38.0^{\circ}\text{C}$ (100.4°F). Temperatures collected in degrees Fahrenheit will be converted to degrees Celsius using (°F – 32) × 5/9.

Statistical Analysis Plan (SAP) BNT165-01

Page 21 of 36 Version: 3.0 Date: 08 MAY 2024

The highest oral temperature for each day will be recorded in the e-diary and the temperature from Day 1 through Day 7 will be graded as described in Table 5.

Solicited systemic reactions will be categorized as mild, moderate, severe or potentially life-threatening) and graded from 1 to 4 as described in Table 5. The categories and grades are based on the FDA Guidance for Industry: "Toxicity Grading Scale for Healthy Adult and Adolescent Volunteers Enrolled in Preventive Vaccine Clinical Trials"⁴. Any systemic reaction of Grade 3 or higher will be confirmed by the investigator along with an assessment if it meets the definition of Grade 4.

Page 22 of 36 Version: 3.0 Date: 08 MAY 2024

Table 5: Systemic reaction grading scale

	Mild (Grade 1)	Moderate (Grade 2)	Severe (Grade 3) ^a	Potentially life- threatening (Grade 4) ^a			
Vomiting	1 to 2 times in 24 h	>2 times in 24 h	Requires intravenous hydration	Emergency room visit or hospitalization for hypotensive shock			
Diarrhea	2 to 3 loose stools in 24 h	4 to 5 loose stools in 24 h	6 or more loose stools in 24 h	Emergency room visit or hospitalization for severe diarrhea			
Headache	Does not interfere with activity	Some interference with activity	Prevents daily routine activity	Emergency room visit or hospitalization for severe headache			
Fatigue / tiredness	Does not interfere with activity	Some interference with activity	Prevents daily routine activity	Emergency room visit or hospitalization for severe fatigue			
Myalgia - muscle pain	Does not interfere with activity	Some interference with activity	Prevents daily routine activity	Emergency room visit or hospitalization for severe muscle pain			
Arthralgia - joint pain	Does not interfere with activity	Some interference with activity	Prevents daily routine activity	Emergency room visit or hospitalization for severe joint pain			
Chills Does not interfere with activity		Some interference with activity	Prevents daily routine activity	Emergency room visit or hospitalization for severe chills			
Fever (oral temperature of ≥38.0°C / ≥100.4°F)	38.0°C/100.4°F to 38.4°C/101.1°F	38.5°C/101.2°F to 38.9°C/102.0°F	39.0°C/102.1°F to 40.0°C/104.0°F	>40.0°C/>104.0°F			

Investigator or medically qualified person confirmation is required.

Systemic reactions (vomiting, diarrhea, headache, fatigue/tiredness, myalgia-muscle pain, arthralgia-joint pain, chills and fever) reported within 7 days after IMP will be summarized in the same manner as local reactions (see Section 8.5.2) using the safety set but excluding subjects without any e-diary data throughout the 7 days after vaccination. Listing of subjects in the safety set, with reported systemic reactions, will be provided.

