8.2.2 Vital signs, height, and body weight

Vital signs (comprising systolic/diastolic blood pressure, pulse rate, respiratory rate, and oral body temperature) will be assessed at the times given in the SoA (Section 1.3).

Vitals signs measurements should be preceded by at least 5 minutes of rest for the trial subject in a quiet setting without distractions (e.g., television, cell phones).

Vital signs will be measured with trial subjects in seated position.

Systolic/diastolic blood pressure, respiratory rate, and pulse measurements will be assessed with a completely automated device. Manual techniques will be used only if an automated device is not available.

Oral body temperature (in °C or °F) will be measured and recorded to one decimal place. Body temperature will be reported in °C.

Height and body weight will be measured in centimeters and kilograms and recorded at screening.

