8.1.1 General definitions

Baseline is defined as last available value prior to first dose of trial IMP.

Generally, if there are multiple pre-baseline assessments available for a particular day, the assessment that is closest to the day (and time if collected) of the first dose of a trial treatment will be used as the baseline value.

Change from baseline: Unless otherwise specified, this will be calculated as follows:

Change from baseline = post-baseline assessment value – baseline assessment value.

If either the baseline or post-baseline assessment value is missing, the change from baseline is set to missing as well.

Body mass index (BMI) will be calculated as follows:

BMI
$$\left(\frac{\text{kg}}{\text{m}^2}\right) = \frac{\text{Weight (kg)}}{\text{Height(m)}^2}$$

Temperatures collected in °F will be converted to °C as follows:

$$^{\circ}C = (^{\circ}F - 32) * 5/9$$

Duration will be calculated as follows:

• Duration = last observation date - first observation date + 1.

For conversion of days to months or years the following rules will be applied:

- 1 month = 30.4375 days
- 1 year = 365.25 days

Trial Day will be calculated as follows:

- If assessment/onset date < date of first IMP dose, then trial day = assessment date
 date of first IMP dose
- If assessment/onset date >= date of first IMP dose, then trial day = assessment/onset date - date of first IMP dose + 1

That is, trial day 1 indicates the date of first IMP dose.

The day relative to dose 2 or dose 3 will be calculated as follows:

Statistical Analysis Plan (SAP)

BNT165-01

Page 14 of 36

Version: 3.0

Date: 08 MAY 2024

 If assessment/onset >= date of second IMP dose and < date of third IMP dose, then day relative to dose 2 = assessment/onset date - date of second IMP dose + 1

If assessment/onset >= date of third IMP dose, then
 day relative to dose 3 = assessment/onset date – date of third IMP dose + 1

All trial data will be presented at the visit in the visit assigned in the Case Report Form (CRF)/visit assigned in external data. No windowing of data for the purposes of assigning to a visit will occur.

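### Two of the paired °C/°F fever limits disagree under the SAP's own conversion formula, so °F diary readings of 101.2 and 102.1 can be graded one step low or left ungraded

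*SAP*

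**What the plan says.** SAP 8.5.3 gives the conversion inside the fever derivation: "Temperatures collected in degrees Fahrenheit will be converted to degrees Celsius using" the formula (°F – 32) × 5/9. SAP 8.1.1 has the same rule among the general definitions: "Temperatures collected in °F will be converted to °C as follows". Directly after the conversion, SAP 8.5.3 says of the daily diary maximum that the "temperature from Day 1 through Day 7 will be graded as described in Table 5".

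Table 5 prints each fever grade in both units:

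- Grade 1: "38.0°C/100.4°F to 38.4°C/101.1°F"
- Grade 2: "38.5°C/101.2°F to 38.9°C/102.0°F"
- Grade 3: "39.0°C/102.1°F to 40.0°C/104.0°F"
- Grade 4: above 40.0°C or 104.0°F

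Protocol Table 3 has the same limits. Protocol 8.2.2, on vital signs, allows either unit, records to one decimal and adds: "Body temperature will be reported in °C".

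Neither document says whether the grade is taken from the °F value as collected or from the converted °C value. Neither gives a rounding rule for the converted value. The decimal-place rules in SAP Appendix 3 concern displayed summary statistics.

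**The concern.** A programmer who follows SAP 8.5.3 in the order written would convert to °C and then look up the grade. For a table printed in two units this is harmless only if the paired limits are equivalent under the stated formula. If a pair is not equivalent, a reading at that limit gets one grade from the °F column and a different grade, or none, from the °C column.

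Solicited systemic reactions are a primary endpoint. They are tabulated by maximum grade, and the overview summary has a separate Grade ≥3 analysis. Each dose level has 16 vaccine recipients, so a single reclassified subject is visible in the table.

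**Working it through.** **Inputs.** The formula is from SAP 8.5.3 and 8.1.1. The six paired limits are from SAP Table 5 and are identical in protocol Table 3. One-decimal readings are an assumption for the diary, borrowed from protocol 8.2.2 on vital signs. Sixteen vaccine recipients per dose level is from SAP 3.2.

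**Step 1: reproduce the printed pairs with °C = (°F – 32) × 5/9.**

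| Printed pair | Calculation | Result in °C | One decimal | Agrees? |
|---|---|---|---|---|
| 38.0 / 100.4 | 68.4 × 5/9 | 38.000 | 38.0 | yes |
| 38.4 / 101.1 | 69.1 × 5/9 | 38.389 | 38.4 | yes |
| 38.5 / 101.2 | 69.2 × 5/9 | 38.444 | 38.4 | **no** |
| 38.9 / 102.0 | 70.0 × 5/9 | 38.889 | 38.9 | yes |
| 39.0 / 102.1 | 70.1 × 5/9 | 38.944 | 38.9 | **no** |
| 40.0 / 104.0 | 72.0 × 5/9 | 40.000 | 40.0 | yes |

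Four of the six pairs reproduce. In reverse, 38.5 × 9/5 + 32 = 101.3°F and 39.0 × 9/5 + 32 = 102.2°F. The two printed °F lower limits are therefore each 0.1°F below the equivalent of their °C partners.

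**Step 2: grade every 0.1°F reading from 99.5 to 105.5°F twice.** The first grade uses the °F column directly. The second uses the °C column after conversion, under each rule a programmer might adopt.

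| Rule for the converted value | 101.2°F (°F column: Grade 2) | 102.1°F (°F column: Grade 3) | Any other reading changed? |
|---|---|---|---|
| Rounded to one decimal | Grade 1 | Grade 2 | no |
| Unrounded, cut at ≥38.5 and ≥39.0 | Grade 1 | Grade 2 | no |
| Unrounded, cut at >38.4 and >38.9 | Grade 2 | Grade 3 | no |
| Unrounded, printed ranges taken literally | no grade | no grade | no |

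In the last row the readings fall in the gaps 38.4 to 38.5 and 38.9 to 39.0. They still meet the SAP's fever definition (38.0°C or above), so such a subject could count as having fever of any grade while that reading falls in none of Grades 1 to 4.

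**Step 3: effect on the categories.** Under the first two rules, the number of tenth-degree °F readings in each grade changes as follows:

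- Grade 1: 8 to 9
- Grade 2: 9 to 9 (it loses 101.2 and gains 102.1)
- Grade 3: 20 to 19

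Grade ≥2 and Grade ≥3 therefore each lose one reading, while Grade 2 as a separate category has no net change. These are counts of scale values, not of subjects.

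**Step 4: size for one subject.** 1/16 = 6.25 percentage points of a dose level's rate.

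**The case against.** The strongest reply is that the SAP never says to grade the converted value. Table 5 carries °F limits for every grade, so a °F reading can be graded directly and converted only for presentation. This stands in part: the order is an inference. It is the natural one, because the general conversion rule is already in 8.1.1 and is repeated in 8.5.3 immediately before the grading step. The text does not settle the matter, and the answer changes the grade.

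A reader might infer more than the documents support:

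- *That the grade always falls.* It does not under the >38.4 and >38.9 cut-offs, and the literal ranges give no grade rather than a lower one. None of the four rules raises a grade.
- *That moderate fever as such is under-counted.* Grade 2 loses one reading and gains another. Only the cumulative Grade ≥2 and Grade ≥3 counts can be said to fall.
- *That Grade 3 fever is lost for good.* Grade 3 or higher must be confirmed by the investigator. SAP 8.5.2.1 uses the investigator's confirmed grade where it differs from the subject's, and 8.5.3 carries the severity derivation over to systemic reactions. A reading of 102.1°F confirmed as Grade 3 at the site may therefore stay Grade 3. The SAP does not say how this override applies to a grade computed from a measured temperature. No confirmation is required at 101.2°F.
- *That cohort pausing decisions are affected.* Protocol 7.1 and 7.1.1 rest pausing on events reported by the sites and reviewed by the IRC, not on grades derived in the analysis dataset.

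It is also fair to say that the trial is descriptive, with no hypothesis tests, and that only two exact readings are involved. The documents do not say how many diary temperatures will be in °F, or how often these two values will occur.

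**Conclusion.** The concern holds in limited form. The SAP's formula and its fever table disagree at 101.2°F and 102.1°F; this is exact arithmetic on the plan's own figures. If fever is graded on the converted value, three of the four rules examined lower the grade or leave it undefined, so Grade ≥2 and Grade ≥3 fever can be under-counted in a primary summary.

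The size is small. A maximum-grade count can change only for a subject whose highest temperature in the diary period is exactly 101.2°F or 102.1°F, collected in °F, and for 102.1°F only if investigator confirmation does not restore Grade 3. Each such subject among 16 is worth 6.25 points.

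The conclusion assumes that conversion precedes grading and that diary readings have one decimal. It takes no position on which of the paired limits is the right one. The correction should be made because the conflict is certain and easily removed, not because a large distortion is expected.

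**What to change.** In SAP 8.5.3, state that the fever grade is assigned from the Table 5 limits in the unit in which the temperature was recorded, and that conversion to °C serves only display and descriptive statistics. State the rounding rule for any converted value, with the grade intervals written so that they leave no gaps. Reconcile the paired °C and °F limits in SAP Table 5 and protocol Table 3, so that both documents carry one consistent scale.

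The SAP part costs a sentence or two and a small programming change. Reconciling the limits also touches the protocol table if the two documents are to stay aligned.

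There is a small downside. Until the limits are reconciled, grading in the recorded unit lets near-identical temperatures receive different grades: 101.2°F would be Grade 2 and 38.4°C Grade 1. The printed table already implies this.
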